#### **10.4.2 Progression-Free Survival**

PFS is defined as the number of days from Visit 1 in Cycle 1 to first PD or death. If no death is observed within this period, PFS will be censored at the last progression assessment. PFS will be derived for all patients and presented graphically as well as summarized using survival analysis methods: distribution functions will be estimated using Kaplan-Meier technique and times will be censored in accordance with Table A in Appendix 3 in the FDA Guidance for Industry: Clinical Trial Endpoints for the Approval of Cancer Drugs and Biologics (2007).

#### **10.4.3 Duration of Response**

DoR is defined as the number of days from the first documentation of objective tumor response (CR or PR) to the date of first PD or death. DoR will be analyzed using the same statistical methodology as PFS.

Document Name: GCT1021-01 Protocol

Document Number: TMF-03326

Version: 11.0

---

#### **10.4.4 Overall Survival**

Overall survival (OS) is defined as the number of days from Visit 1 in Cycle 1 to death. OS will be analyzed using the same statistical methodology as PFS and DoR except that censoring will not be applied neither when visits are skipped nor when new anti-cancer therapies are given.

#### **10.4.5 Tumor Shrinkage**

Tumor shrinkage (based on CT-scan evaluations) will be listed and summarized, per source (radiologist, central read).

#### **10.4.6 Statistical Methodology for Pharmacokinetics Data**

Individual curves of plasma/serum concentration of enapotamab vedotin, HuMax-AXL and free toxin (MMAE), including information on actual dose, will be presented for all patients. All available data will be shown in these figures.

The following PK parameters will be calculated based on non-compartmental methods: clearance, volume of distribution and AUC ( $AUC_{0-Clast}$  and  $AUC_{0-\infty}$ ),  $C_{max}$ ,  $T_{max}$ , pre-dose values, and half-life. The PK parameters will be calculated separately per treatment cycle.

The relation between derived PK parameters and covariates such as actual dose, weight and dose, selected laboratory parameters will be evaluated graphically.

If deemed applicable compartmental modelling approaches to parameter estimation will be applied.

Furthermore, a population PK model will be developed before starting the 3Q4W-arm. The model will be updated during the trial. Details of these analyses are provided in a separate population PK analysis plan (██████████).

Further exploratory analyses of PK data may be performed.

### **10.5 Handling of Missing Data or Outliers**

No imputation of missing data is planned for safety endpoints and PK endpoints. If outliers are detected, a robustness analysis where the outlier effect is reduced or eliminated may be considered.

### **10.6 Subgroups and Site Effects**

Subgroup analyses for the following factors are planned:

- Cancer type
- ADA-positivity (only for  $\geq$  Grade 3 AEs and tumor shrinkage endpoints)

Document Name: GCT1021-01 Protocol

Document Number: TMF-03326

Version: 11.0

---

Other sub-group analyses may be performed post hoc. Due to the low expected number of patients per site no investigation of side effects are planned.

### **10.7 Interim Analyses**

Protocol Amendment 9 (v 10.0) allowed for exploratory analysis of subsets of data.

In November 2020, Genmab decided to discontinue development of enapotamab vedotin but continue to offer treatment to patients who are deriving clinical benefit in the present trial. At the time of this amendment (Amendment 10), the dose escalation part and the enrollment of the dose expansion part of the trial have been completed with only 3 patients active on trial treatment. The 3 patients have been on treatment for at least 7 months, which is considered sufficient time to evaluate efficacy and safety. An analysis is therefore planned, i.e. data collected up to and including the data cutoff date will be included in the CSR. Furthermore, limited AE and SAE data from data cutoff to the time of database lock for the three active patients will be included. Data collected after the data cutoff date until the end of trial will be reported in an addendum to the CSR, once the trial is completed.

From time of approval of this protocol amendment to end of trial no further information is being collected for patients in patient follow-up.

The reporting of the trial will be based on a locked database with clean data up to the cutoff point.

Final lock will be done at end of trial.

### **10.8 Clinical Trial Reporting**

Data collected up to and including the data cutoff date will be included in the CSR. Data collected after the data cutoff date until the end of trial will be reported in an addendum to the CSR, once the trial is completed.

### **10.9 Sample Size Estimation**

The estimates and calculations in this section are all performed in SAS V9.4.

Document Name: GCT1021-01 Protocol

Document Number: TMF-03326

Version: 11.0

**10.9.1 Dose Escalation**

[figure not shown]
In the dose-escalation 1Q3W-arm, 28 patients are expected and the maximum number of patients is set to 41. The dose-escalation 3Q4W-arm will be including 15-36 patients. The expansion cohorts will include up to 349 patients. The information obtained from the above patients is considered adequate to provide sufficient basis for the planning and design of further trials.

For the dose escalation part, no formal sample size calculation has been performed. For the 1Q3W-arm, the operating characteristics of the mCRM-design are described in details in [REDACTED] and [REDACTED]. For the 3Q4W-arm, effect of the 3+3 design on estimates-precision is presented below:

The probability of making at least 1 observation of an event with rare incidence.

The widths of two-sided 95% confidence intervals for incidences of AEs, based on an exact binomial distribution.

**Table 27. Impact of Sample Size on Descriptive and Inferential Statistics for Dose-Escalation 3Q4W**

[figure not shown]
Document Name: GCT1021-01 Protocol

Document Number: TMF-03326

Version: 11.0

### 10.9.2 Expansion

Table 28. Impact of Sample Size on Descriptive and Inferential Statistics for Endpoints in the Expansion Part

The widths of the confidence intervals apply to binary endpoints of both safety (e.g., AE) and efficacy (e.g., response) nature.

For the test of the null hypotheses (cf. Section 10.2.3): e.g., assuming  $\pi_{response}=30\%$ , the probability of rejecting the null hypothesis  $H_0: \pi_{response} \leq 0.10$  is 69% when N=22.

The sample size in this exploratory trial has not been determined based on a formal power analysis. A power analysis of various assumptions of  $H_{0,i}$  and  $H_{alt}$  is presented in Table 29.

Document Name: GCT1021-01 Protocol

Document Number: TMF-03326

Version: 11.0

**Table 29. Power Analysis of the Expansion Part**

$H_0$	$H_{alt}$	Power N=22	Power N=30	Power N=37	Power N=45	Power N=82	Power N=202	Power N=349
0.10	0.25	48%	65%	74%	83%	97%	100%	100%
	0.30	69%	84%	91%	95%	100%		
	0.35	84%	94%	97%	99%	100%		
	0.40	93%	98%	99%	100%	100%		
0.15	0.25	30%	33%	45%	45%	69%	97%	
	0.30	51%	57%	71%	74%	93%	100%	
	0.35	70%	78%	88%	91%	99%		
	0.40	84%	91%	97%	98%	100%		

Power=  $P(\text{reject } H_0 | H_{alt})$ , no stopping in interim analysis, calculated using PROC POWER.**Table 30. Operating characteristics in the futility analyses (stop recruiting if  $\leq 2/22$  or  $\leq 3/22$  responders)**

ORR to beat ( $H_0$ )	$H_{alt}$	P[Stop early   $H_0$ ] (N=22)	P[Stop early   $H_{alt}$ ] (N=22)	Statistical Power (N=22+8)	Statistical Power (N=22+15)	Statistical Power (N=22+60)
Stop if $\leq 2/22$ responders						
0.10	0.25	0.62	0.06	65%	73%	92%
0.10	0.35	0.62	0.006	94%	97%	99%
0.15	0.25	0.34	0.06	33%	45%	67%
0.15	0.35	0.34	0.006	77%	88%	99%
0.20	0.25	0.15	0.06	11%	11%	22%
0.20	0.35	0.15	0.006	49%	55%	88%
Stop if $\leq 3/22$ responders						
0.15	0.25	0.57	0.16	33%	44%	63%
0.15	0.35	0.57	0.025	77%	88%	97%
0.20	0.25	0.33	0.16	11%	11%	21%
0.20	0.35	0.33	0.025	49%	56%	87%

The estimates in [Table 30](#) are based on 120000 simulations of clinical trials with the corresponding stopping rule for futility incorporated in the interim analysis. The one-sided test in the final analysis is performed on the 5% significance level.

Document Name: GCT1021-01 Protocol

Document Number: TMF-03326

Version: 11.0

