### 3.4 Number of Patients and Sites

In total, approximately 426 patients can be enrolled in this trial. Assuming an anticipated screen failure rate of 30%, up to 609 patients can be screened.

Up to 41 patients are planned to be enrolled in the 1Q3W dose escalation.

Between 15 and 36 patients are planned to be enrolled in the 3Q4W dose escalation depending on the number of dose levels during the dose escalation.

In the expansion part, approximately 349 patients can be enrolled in 8 cohorts:

In Cohorts 1, 3, 4, 5 and 7, the aim is to enroll 22 patients per cohort; however, in order to obtain evaluable fresh tumor biopsies from at least 15 patients per cohort, up to 15 patients may be additionally recruited per cohort leading to a maximum of 37 patients enrolled per cohort.

Document Name: GCT1021-01 Protocol

Document Number: TMF-03326

Version: 11.0

An efficacy signal has been observed in NSCLC patients without EGFR/ALK mutations, therefore up to 60 additional patients will be enrolled into the NSCLC Cohort 2 (Table 1) to further understand the safety, tolerability, efficacy and biomarker findings of enapotamab vedotin in this population of patients; the aim is therefore to enroll a total of up to 82 patients in Cohort 2. [REDACTED]

A sub-group of the patients in Cohort 2 (up to 30 patients), may be enrolled on a dose of 1.8 mg/kg to further understand the tolerability profile and to extend the therapeutic window of enapotamab vedotin. Enapotamab vedotin belongs to valine-citrulline-monomethyl auristatin E (vc-MMAE) class of ADC, and peripheral neuropathy is a known side-effect of MMAE and a potential dose limiting toxicity (DLT). It has been shown in a pooled time-to-event analysis across eight vc-MMAE ADCs, that peripheral neuropathy events (Grade  $\geq 2$ ) were higher in patients with higher ADC exposure. The MTD/RP2D in ADC-vc-MMAE ranges from 1.8 mg/kg to 2.4 mg/kg. Given the identical cytotoxic payload of MMAE and the similar safety profile observed for enapotamab vedotin as compared to other ADC-vc-MMAEs, 1.8 mg/kg dose is expected to have a better tolerability profile. [REDACTED]

Furthermore, if considered necessary (as assessed by the DMC and the sponsor safety committee) selected cohort(s) might be explored on both dosing schedules from the dose escalation without increasing the total number of patients to be included in the trial.

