Overall, the 1.0 mg/kg 3Q4W schedule is anticipated to provide a favorable balance of anti-tumor activity with an acceptable safety profile.

An interim analysis for futility will be performed after 22 patients per cohort (minus Cohorts 6 and 8) if there are < 15 patients with evaluable fresh biopsies in the corresponding cohort. If too few responders are observed, further recruitment to the corresponding cohort may be stopped, refer to Section 10.7 for more details. However, if the required number of biopsies as well as responders (see Table 1) have been observed before the futility analysis in the corresponding cohort, the futility analysis can be cancelled.

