### 10.2.3 Expansion Part

The results from the expansion phase will be presented using summary statistics. For each cohort,

Document Name: GCT1021-01 Protocol

Document Number: TMF-03326

Version: 11.0

---

the number of responders will be evaluated. Let  $\pi_{response,i}$  denote the proportion of responders in cohort  $i$ , where  $i=1, 2, 3, 4, 5$  or  $6$ . The null hypothesis  $H_{0,i}: \pi_{response,i} \leq 0.10$  will be tested against the one-sided alternative hypothesis  $H_{alt,i}: \pi_{response,i} > 0.10$ , for Cohorts 1-6 and Cohort 8, using the exact binomial test on the 5% significance level, for both confirmed as well as unconfirmed response. The null hypothesis for the platinum-resistant ovarian cancer patients in Cohort 7  $H_{0,7}: \pi_{response,7} \leq 0.15$  will be tested against the one-sided alternative hypothesis  $H_{alt,7}: \pi_{response,i} > 0.15$ . Patients receiving different dosing regimens will be analyzed separately from each other.

With a minimum follow up of at least 7 months for all patients, the analysis per CSR cutoff is considered the full efficacy results. Any data collected after the CSR cutoff will be presented in data listings in the CSR addendum.

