For the dose-escalation part, all seven dose levels from the 1Q3W regimen together with a 'total' will be presented on one page. And similar for the 3Q4W regimen in the dose-escalation part, all four dose levels will be presented together on one page including a 'total'.

For the expansion part the following grouping should be done: Cohorts 1, 3, 4, 5, 6 and 7 on one page and cohort 2 with 2.2 mg/kg, cohort 2 with 1.8 mg/kg, cohort 2 total, cohort 8, total across 1Q3W and total across 3Q4W on one page.

All data will be listed by trial part, cohort for expansion part, dose schedule, dose level, subject number and visit (if applicable).

In general, in plots where subject data are grouped together (e.g. plots of means), the ticks on the time-axis will denote the nominal visit numbers (e.g. Scr, C1D1, C1D2, C1D4 etc.) separated with distances proportionate to the difference between the time-points of the corresponding visits in the relevant dose schedule (cf. the Visit Number and Day/Week rows of table of assessments in section 8 of the protocol final version 10.0, dd. 9 December 2019). Unscheduled visit data will not be included. In plots where individual subject data are plotted vs. time, the time on the horizontal axis will denote the actual time since C1D1. Unscheduled visit data will be included in these plots.

In tables and listings presenting data by visit, the visit names (Screening, Cycle 1 Day 1, Cycle 1 Day 2, ..., End of Treatment, Safety Follow-up, Subject Follow-up and End of Trial) will be used or their abbreviated term (Scr, C1D1, C1D2, ..., EOTrt, Saf FU, Pat FU, EOTrial).

In tables and listings presenting coded data (medical history, prior and concomitant medications, adverse events, prior and subsequent cancer therapies), the dictionary and the version used will be mentioned in the footnote.

When data until a certain date needs to be included in the analysis, the cut-off date will be defined as this date. If no cut-off needs to be applied, the cut-off date will be defined as the date of data extraction.

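### Do the power tables overstate Cohort 2's power by treating its maximum of 82 as a single test when two dose groups are to be analysed separately?

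*Protocol*

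**What the plan says.** Section 3.4 of the protocol sets the size of Cohort 2: "the aim is therefore to enroll a total of up to 82 patients in Cohort 2". That is the 22 common to most cohorts plus up to 60 more. The same section adds: "A sub-group of the patients in Cohort 2 (up to 30 patients), may be enrolled on a dose of 1.8 mg/kg". These patients are part of the 82 and not additional to it.

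Section 10.2.3 tests each cohort's response rate against a null of 10% (15% in Cohort 7), one-sided, "using the exact binomial test on the 5% significance level". It then says: "Patients receiving different dosing regimens will be analyzed separately from each other".

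Section 10.9.2 gives power by sample size. Table 29 has columns for N = 22, 30, 37, 45, 82, 202 and 349 without a futility stop. Table 30 adds the stop at 22 patients for 22+8, 22+15 and 22+60, the last in the column headed "Statistical Power (N=22+60". The text above the tables says: "The sample size in this exploratory trial has not been determined based on a formal power analysis".

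For display, SAP Section 4 (General Analysis Definitions) lists these groups among its columns: "cohort 2 with 2.2 mg/kg, cohort 2 with 1.8 mg/kg, cohort 2 total, cohort 8".

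**The concern.** Among single cohorts, only Cohort 2 has a maximum of 82, so a reader will take the N=82 and 22+60 columns as its power. If some of the 82 are treated at 1.8 mg/kg and the doses are tested separately, neither dose-level test has 82 patients. With the sub-group at its limit of 30, the 2.2 mg/kg test has 82 − 30 = 52. Neither table has an entry for 52 or 22+30, and nothing says that the N=82 columns assume one dose or pooling. The N=30 column would fit a full 1.8 mg/kg group but is not identified as doing so.

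What would be at stake is interpretation. Cohort 2 was enlarged because of an efficacy signal, so its power figures are likely to be consulted. Someone weighing a non-significant result in one dose group might cite 97% or 92% when the figure for that group is lower. At a 25% response rate the chance of missing the effect at 2.2 mg/kg would be about 13% (100 − 87.1) and not about 3% (100 − 96.7). For a full 1.8 mg/kg group it would be about 35% (100 − 65.2).

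**Working it through.** **Inputs.** Null rate p0 = 0.10, one-sided exact binomial test, alpha 0.05 (Sections 10.2.3 and 10.9.2). Alternative 0.25 (first row of Tables 29 and 30) and 0.30 (the worked example in Section 10.9.2). Futility stop at 2 or fewer responders in 22 (Table 1). Cohort 2 maximum 82, with up to 30 at 1.8 mg/kg (Section 3.4).

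**Formulas.**
- Critical value r: the smallest r with P(Bin(N, 0.10) ≥ r) ≤ 0.05.
- Power without a stop: P(Bin(N, p1) ≥ r).
- Power with a binding stop: the sum over x = 3 to 22 of P(Bin(22, p1) = x) × P(Bin(N − 22, p1) ≥ r − x).

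**Reproducing the plan's figures (10% against 25%).**
- N = 22, 30, 37, 45: 48.3%, 65.2%, 74.1%, 82.8% (tabulated 48, 65, 74, 83%).
- N = 82: r = 14, exact alpha 0.0324, power 96.7% (tabulated 97%).
- 22+8, 22+15, 22+60: 65.1%, 73.3%, 91.7% (tabulated 65, 73, 92%).
- Probability of an early stop: 0.620 under the null and 0.061 at 25% (tabulated 0.62 and 0.06).

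The tabulated entries are therefore right for the N they state.

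**The 2.2 mg/kg test if 82 are enrolled.**

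| At 1.8 mg/kg | N at 2.2 mg/kg | r | Power at 25%, no stop | Power at 25%, binding stop | Power at 30%, no stop |
|---|---|---|---|---|---|
| 0 | 82 | 14 | 96.7% | 91.7% | 99.8% |
| 10 | 72 | 13 | 93.7% | 89.4% | 99.3% |
| 20 | 62 | 11 | 93.3% | 89.3% | 99.1% |
| 30 | 52 | 10 | 87.1% | 84.4% | 97.2% |

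The largest losses at 25% are 96.7 − 87.1 = 9.6 points without the stop and 91.7 − 84.4 = 7.3 points with it. At 30% the loss is 99.8 − 97.2 = 2.6 points. N = 52 gives the lowest power at 25% of any N from 52 to 82. Exact power does not fall smoothly: with 26 at 1.8 mg/kg, N = 56 has 92.2%.

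**The 1.8 mg/kg test.** At N = 30, r = 7 and power is 65.2% at 25% and 84.0% at 30%. Both are already in Table 29 as 65% and 84%.

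**What a reader can get from the existing table.** The nearest tabulated N below 52 is 45, with 83% at 25% and 95% at 30%. Both are lower than the N = 52 values of 87.1% and 97.2%, so reading down to N = 45 errs on the cautious side.

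**The case for a change.** The case for a change rests on Section 10.9.2 tying its power figures to the test in Section 10.2.3. That test is done by regimen, 82 matches Cohort 2's maximum alone, and the remedy would be one footnote and two entries. All of that is factually right. If the split is used, Section 10.2.3 specifies no dose-level test with 82 patients, and the label is missing.

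Four things limit its weight.

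- The tables are a grid of power by N. Section 10.9.2 presents Table 29 as covering various assumptions. It includes N = 202, which is no cohort's maximum, and N = 349, the expansion total. Table 30 includes a null of 20%, which no cohort uses. Such a grid need not list every sample size that could occur.
- A whole-cohort reading is not foreign to the plan. Section 10.2.3 indexes its hypotheses by cohort, and the SAP gives Cohort 2 a total column beside the two dose columns. That column is a display grouping and not a specified pooled test, so this point answers only part of the objection.
- The 87% needs 82 enrolled and all 30 optional places at 1.8 mg/kg filled. The 84% also needs the first 22 all at 2.2 mg/kg and a stop that binds. The documents do not say how the look treats mixed doses. It takes place only if fewer than 15 evaluable fresh biopsies are available, and Section 3.4 says only that "further recruitment to the corresponding cohort may be stopped".
- Nothing depends on the entry. Power did not set the sample size, and Section 10.7 records that expansion enrolment is complete. Actual group sizes are therefore fixed, and a non-significant result is better read from the observed rate and its interval than from a planned power for a hypothetical 52/30 split.

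**Conclusion.** No change is needed. The N=82 and 22+60 entries are correct for a single-dose or pooled Cohort 2 test. What is missing is a label and one further sample size in an illustrative grid, and a statistician reading power for a dose group will use that group's own N.

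In the worst case, with 30 of 82 at 1.8 mg/kg and a 25% response rate, the 2.2 mg/kg test has 87.1% power against the tabulated 97%. With a binding stop and the first 22 all at 2.2 mg/kg it has 84.4% against 92%. At 30%, without the stop, it has 97.2%. The full 1.8 mg/kg group has 65%, which Table 29 already shows under N=30. These figures assume the protocol's one-sided exact test at 5% against a 10% null.

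The critical values, the tests, the futility rule and the results are the same whether or not the tables carry the extra entries. A footnote would do no harm, but it would alter no decision or conclusion.

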### 10.9.3 Statistical Power in Exploratory Analyses in the Expansion

The power estimates (Figure 5) are based on 4000 simulations of exploratory analyses, with e.g., the ones in Section 10.3.11 in mind. The simulations estimate the power in detecting a relation between two uniformly distributed variables (%response and biomarker expression both ranging from 0% to 100% to in general represent any kind of response and expression) with correlation  $\rho_{Pearson}$  between them, either by correlation analysis or logistic regression. The analyses are performed on the 5% significance level. For the logistic regression, the responder-variable is based on a dichotomization of the %response-variable: responder = yes if the %response  $\geq 30\%$  and responder = no if the %response  $< 30\%$ .

[figure not shown]

Figure 5. Statistical power in exploratory analyses

E.g., if data from 202 patients are available, the power in detecting a correlation between % tumor reduction and Axl-expression would be  $\approx 79\%$  if the correlation between them is  $= 0.20$ . And when the correlation  $= 0.30$  and the (objective) response rate is  $30\%$ , the power in finding a relationship between (objective) response and Axl-expression by means of logistic regression is approximately  $88\%$ .

Document Name: GCT1021-01 Protocol

Document Number: TMF-03326

Version: 11.0

---

## **11. TRIAL OPERATIONS**

### **11.1 Countries**

The trial is expected to be conducted in Denmark, Belgium, UK, US, the Netherlands and Spain. More countries may be added.

### **11.2 Number of Sites**

In the dose escalation part 3-6 sites will participate and the number of sites will be increased up to 60 sites for the expansion part. Please refer to Section 3.4.

## **12. QUALITY CONTROL AND QUALITY ASSURANCE PROCEDURES**

### **12.1 Monitoring of the Trial and Regulatory Compliance**

The CRO project manager, or designee, will make a site initiation visit at each site to review the protocol and its requirements with the Investigator(s), inspect the enapotamab vedotin storage area, and fully inform the Principal Investigator of his/her responsibilities and the procedures for assuring adequate and correct documentation. During the site initiation visit the eCRFs will be reviewed. Other pertinent trial materials will also be reviewed with the Investigator's research staff.

During the course of the trial, the monitor will make regular site visits in order to review protocol compliance, examine eCRFs, and individual patient's medical records and assure that the trial is being conducted according to pertinent regulatory requirements as well as GCP. All eCRF entries will be verified with source documentation. The review of medical records will be done in a manner to assure that patient confidentiality is maintained. In accordance with applicable national and local regulations, monitors, investigators and the sponsor's (or their designee's) will only have access to information relevant to the trial.

Representatives of the sponsor's clinical quality assurance department may visit the trial site at any time during or after completion of the trial to conduct an audit of the trial in compliance with regulatory guidelines and company policy. These audits will require access to all trial records, including source documents, for inspection and comparison with the eCRFs. Patient privacy must, however, be respected. The investigator and trial-site personnel are responsible for being present and available for consultation during routinely scheduled trial-site audit visits conducted by the sponsor or its designees.

Similar auditing procedures may also be conducted by agents of any regulatory body, either as part

Document Name: GCT1021-01 Protocol

Document Number: TMF-03326

Version: 11.0

---

of a national GCP compliance program or to review the results of this trial in support of a regulatory submission. The investigator should immediately notify the sponsor if he or she has been contacted by a regulatory agency concerning an upcoming inspection.

